# Study Aims

The objective of this study is to assess pharmacokinetics of ketamine in the women immediately post cesarean delivery or women weaning from breastfeeding. Study Hypotheses: Breastmilk secretion of ketamine is low and poses minimal risk for neonatal exposure

Study Aims:

Aim 1. Evaluate breastmilk secretion of ketamine and its metabolites during and after administration of intravenous ketamine infusion in women immediately post C-section or women weaning from breastfeeding

Aim 2. Quantify pharmacokinetics of ketamine infusion in lactating people

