**3. Describe the primary and secondary study endpoints:**

Primary outcome: Breastmilk transfer: concentration of ketamine and its metabolites in breastmilk

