**4. List the inclusion criteria:**

Cesarean Section Population:

Adult female patients (i.e., ≥18 years of age)

Able to provide informed consent

Cesarean Delivery, Scheduled or Non-Emergent (delivery within 15 minutes not necessary),

ASA PS 2 or 3, with or without E designation (delivery within 15 minutes not necessary)

Spinal anesthesia with intrathecal morphine

Multimodal postop analgesia with IV ketorolac, PO NSAID, and PO APAP

Women who do not plan to breastfeed or who want to temporarily withhold breastfeeding

Weaning Women Population:

Adult female patients (i.e., ≥18 years of age)

Able to provide informed consent

Female weaning baby off of breastfeeding

ASA PS 1, 2 or 3

Minimum production of 2mL/24 hours breast milk

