**Pharmacokinetics and Pharmacodynamic Data
Analysis Plan PART 1**

For

PROTOCOL: NCT04037085 and FDAAA801

STUDY TITLE:

**Ketamine to Improve Recovery After Cesarean
Delivery – Part 1**

(KINETIC)

VERSION 2.0

DOCUMENT DATE: 11/20/2022

I. Clinical Protocol

In a prospective, open label, observational design study, women who were weaning from breastfeeding were enrolled. Women were included if they were ≥ 18 years of age, able to provide informed consent, weaning from breastfeeding, ASA physical status 1, 2, or 3, and producing a minimum of 2mL breast milk every 24 hours. They were excluded if they were allergic to study medications, ASA physical status 4 or greater, had a history of psychiatric comorbidity, uncontrolled hyperthyroidism, cardiac disease, fever, hypertension, history of hallucinations, alcohol, or illicit substance abuse, were on chronic opioid therapy, or had chronic pain disorders.

II. Dose Administration

Subjects received a sub-anesthetic ketamine infusion at 0.1 mg/kg/hour for 12 hours (not to exceed 8mg/hr dose). The justification for intravenous administration for 12 hours of 0.1mg/kg/hr are based on pharmacokinetic studies in humans¹⁸⁻²⁰. Ketamine produces analgesia at plasma concentrations of 100-200ng/mL, which is a fraction of the plasma concentrations associated with general anesthetic doses (9000-25,000 ng/mL)^{18,19}. In longitudinal studies reporting ketamine infusions from 0.05 -1mg/kg/hr, significant reductions in pain scores with minimal adverse events and no psychomimetic effects were observed over infusions lasting up to 5 days, while the effect of ketamine on pain scores were notably varied according to infusion duration^{21,22}.

III. PK Sampling Schedule of Treatment Group

Blood samples (2-3mL each) were collected at 8, 10, 12, 12.5, 13, 14, 16, and 20 hours after ketamine infusion start. Plasma was obtained by centrifugation at room temperature and kept frozen until analysis. The entire human milk expressed was collected starting at the time of infusion initiation (t_0) and ending 12 hours after the infusion was stopped (t_{24}). Breastmilk was labeled by collection time and weighed to estimate the volume (1 gram = 1 mL) and stored at -80°C until analysis. Patient vital signs were monitored every hour and continuous pulse oximetry was done for 12 hours during the infusion and for 12 hours after infusion.

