The pharmacokinetic parameters were calculated using Phoenix™ WinNonlin 8.3.4 (Certara, Princeton NJ). A two compartment PK model was used to estimate PK parameters of ketamine. These parameters included Area Under the Curve (AUC) estimates, the elimination half- life ($t_{1/2}$), clearance (CL), Area Under Moment Curve (AUMC), Mean Residence Time (MRT) and Volume Distribution Steady State (V_{dss}). Statistics will include Mean, Standard deviation (SD), and range where applicable.

- a. **Area Under the Curve (AUC)** is defined as the area under the concentration-time curve. AUC was calculated by linear trapezoidal method.
- b. **Elimination half-life ($t_{1/2}$)** is the time required for drug concentration to decrease by one-half at the end drug dosing. Elimination half-life was obtained from the slope of terminal elimination phase.
- c. **Clearance (CL)** is calculated as the Dose/ $AUC_{0-\infty}$ and calculated by Phoenix WinNonlin.

- d. **Volume Distribution Steady State (Vdss)** is the period of dynamic equilibrium of the drug calculated as the amount of drug in the body at time, t divided by the plasma concentration of the drug at time, t. These data were calculated by Phoenix WinNonlin.
- e. **Metabolic ratio** was calculated for each metabolite using the formula:

$$\text{Metabolic ratio} = \frac{\text{Metabolite } AUC_{0-\infty}}{\text{Parent } AUC_{0-\infty}}$$

VI. Milk to Plasma Ratio

Milk to plasma ratio for KET, NKET, and DHNK were calculated by dividing the concentration of the respective components Ketamine and Ketamine metabolites in human milk by plasma concentration at the corresponding times (± 30 min). Ratios higher than 1 indicate breastmilk concentrations of ketamine and the metabolites would be higher in breastmilk than in maternal plasma concentrations.

VII. Relative Infant Dose (RID) Calculations

The relative infant dose was calculated from the concentrations of ketamine and its metabolites in breast milk at different times following ketamine administration to the women. The concentration of ketamine and its metabolites were converted to amount by multiplying with the volume of breast milk collected at various time intervals. The cumulative dose of ketamine and molar equivalents of metabolites was calculated and RID was calculated using the formula²³⁻²⁵: An RID $\leq 10\%$ was considered low²⁴.

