$$RID (\%) = \text{Cumulative infant dose via breast milk} \left(\frac{\text{mg}}{\text{kg}} \right) \times 100 \div \text{maternal dose} \left(\frac{\text{mg}}{\text{day}} \right)$$

VIII. Descriptive Statistics

Descriptive Statistics will include participant characteristics such as maternal age, maternal race, gravida, parity, ASA rating, and weight. Means and standard deviations (SD) are calculated for maternal age and weight. Medians and range are used for maternal gravida, parity, and ASA rating. Maternal race is noted as a proportion of the total sample.

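### The relative infant dose uses the milk volume weaning women expressed, not what an infant drinks, so it rises and falls with maternal output

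*SAP*

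**What the plan says.** SAP section VII turns milk concentrations of ketamine and its metabolites into amounts: they are "converted to amount by multiplying with the volume of breast milk collected at various time intervals". The amounts, with metabolites as molar equivalents, are summed. The sum enters the RID formula as "Cumulative infant dose via breast milk", in mg/kg, over the maternal dose. A result of 10% or less is classed as low.

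SAP section III defines the volume: "The entire human milk expressed was collected starting at the time of infusion initiation", continuing to 12 hours after the infusion stopped, with volume taken from weight. SAP section I says the women analysed were weaning and qualified by "producing a minimum of 2mL breast milk every 24 hours". The protocol's inclusion criteria for weaning women set the same floor: "Minimum production of 2mL/24 hours breast milk".

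Neither document states an infant milk intake, an infant weight, or any scaling of the collected volume to a feeding infant.

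The protocol's primary outcome is the "concentration of ketamine and its metabolites in breastmilk". RID is not a listed protocol endpoint. The study hypothesis is "Breastmilk secretion of ketamine is low and poses minimal risk for neonatal exposure", and the Brief Description says Part 1 will inform whether breastfeeding pairs are admitted to Part 2.

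**The concern.** RID is meant to describe the dose a breastfed infant would receive. A weaning woman's 24-hour output is a different quantity and may be far smaller. With collected volume in the numerator, two women with identical milk concentrations get RIDs in the ratio of their volumes, although drug transfer into milk is the same.

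RID is the SAP's only measure of infant exposure and the only result set against a safety cut-off. (The milk-to-plasma ratio is compared with 1, but only as an interpretation.) For a woman near the entry floor, the 10% criterion cannot realistically fail, so a low RID there says little about a fed infant. The figure could still be read as support for the hypothesis of minimal neonatal exposure.

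**Working it through.** The documents give no RID value, milk volume, infant weight or infant intake, so there is no figure to reproduce. The check compares the SAP's method with an intake-based one at the same milk concentration.

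**Inputs from the documents**
- Maternal dose D: 0.1 mg/kg/h × 12 h = 1.2 mg/kg (SAP section II).
- Dose cap: "not to exceed 8mg/hr dose", so at most 8 × 12 = 96 mg. It applies above 8 / 0.1 = 80 kg.
- Entry floor for output: 2 mL per 24 h.
- Cut-off: 10%.

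**Assumptions**
- Milk concentration C = 100 ng/mL (0.1 mg/L), one analyte, constant over 24 h. This is the top of the assay's linear range (SAP section IV) and the lower end of the analgesic plasma range in SAP section II. Carrying that plasma range (100–200 ng/mL) over to milk assumes a milk-to-plasma ratio of 1.
- Infant weight W = 4 kg.
- Infant intake I = 150 mL/kg/day, range 100–200.
- Denominator read as mg/kg/day. The SAP prints mg/day, which is a separate fault.

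**Formulas**
- SAP method: RID = 100 × (C × V / W) / D, where V is the collected volume.
- Intake-based: RID = 100 × (C × I) / D.
- Understatement factor: I × W / V. It does not depend on C or D.

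**Intake-based result.** 100 × (0.1 × 0.150) / 1.2 = 1.25%. At 100 and 200 mL/kg/day it is 0.83% and 1.67%. The 10% line is reached at C = 0.1 × 1.2 / 0.150 = 0.8 mg/L = 800 ng/mL (1,200 and 600 ng/mL at 100 and 200 mL/kg/day).

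**SAP method.** Example at 2 mL: 0.1 mg/L × 0.002 L = 0.0002 mg; / 4 kg = 0.00005 mg/kg; / 1.2 × 100 = 0.0042%.

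| Collected in 24 h | RID by SAP method | Implied intake V/W (mL/kg/day) | Factor too low at 150 (100–200) mL/kg/day | Milk concentration needed for RID 10% |
|---|---|---|---|---|
| 2 mL | 0.0042% | 0.5 | 300 (200–400) | 240,000 ng/mL |
| 50 mL | 0.104% | 12.5 | 12 (8–16) | 9,600 ng/mL |
| 200 mL | 0.417% | 50 | 3 (2–4) | 2,400 ng/mL |
| 600 mL | 1.25% | 150 | 1 (0.67–1.33) | 800 ng/mL |

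At 150 mL/kg/day the error is zero at 600 mL (450 mL for a 3 kg infant) and reverses above that. SAP section II gives general-anesthetic plasma levels as 9,000–25,000 ng/mL. At 50 mL the SAP's RID would reach 10% only with milk inside that range, and at 2 mL only with milk well above it.

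**Would the classification change?**
- One analyte at 200 ng/mL: 2.5% (1.67–3.33%).
- Three analytes at 100 ng/mL each. Molar factors from the precursor ions in SAP section IV (m/z minus 1) are 1, 236.84/222.9 = 1.063 and 236.84/220.9 = 1.072, sum 3.135. RID = 1.25% × 3.135 = 3.9% (2.6–5.2%).
- Three analytes at 200 ng/mL each: 7.8% (5.2–10.4%).
- The same for a 100 kg woman, whose capped dose is 96/100 = 0.96 mg/kg: 7.84% × 1.2/0.96 = 9.8% at 150 mL/kg/day.

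Only stacked high-end assumptions reach or approach 10%.

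**The case against.** The other side accepts the text and the arithmetic and contests the weight of the point.

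- **The floor is not an observed volume.** True. The 300-fold figure applies only at the 2 mL minimum. Actual volumes are unknown, and output above intake would reverse the error. The 50 mL and 200 mL rows show the mechanism does not depend on the floor.
- **The percentages are illustrative.** True. Milk levels need not match the cited plasma range, and the infusion stops halfway through the collection. The understatement factors are unaffected, because concentration cancels.
- **A first-day newborn may drink less than 100 mL/kg/day.** This stands, and it matters because the hypothesis concerns neonates. From the table, for a 4 kg infant, a 50 mL collection is correct at an intake of 12.5 mL/kg/day and overstates RID below that. A low-intake case belongs in the sensitivity analysis. The SAP's figure still follows output rather than intake.
- **The expressed amount has a use.** If expression was complete, it is what was available to that woman's own infant. It is worth reporting under that name, but it is not a general RID.
- **The consequence is small.** Largely right. The primary outcome and the milk-to-plasma ratio do not depend on volume, RID is not a listed protocol endpoint, and neither document makes RID the decision rule for Part 2. This limits the severity but does not make the calculation correct.
- **The RID formula is cited to references.** The SAP's own text specifies collected volume, so a citation does not change the stated method.

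**Conclusion.** The concern holds. As written, RID is proportional to the milk each woman expressed and is understated by the factor collected volume / infant intake whenever output is below intake. For a 4 kg infant drinking an assumed 150 mL/kg/day, that is 12-fold at 50 mL and 3-fold at 200 mL, with 300-fold as the extreme at the entry floor. The size in this sample cannot be known from the documents. The proportionality assumes only that concentration is held fixed.

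The reported RID would be wrong as a measure of infant exposure, and the margin below 10% would look wider than it is. The low classification itself would probably survive correction. This should be fixed, but it does not threaten the primary outcome.

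**What to change.** Redefine RID in SAP section VII:

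1. Infant dose (mg/kg/day) = 24-hour time-weighted average milk concentration, ketamine plus molar-equivalent metabolites, × a pre-stated intake per kg per day matched to the infant of interest. For example, use 150 mL/kg/day with 100 and 200 as sensitivity values, plus a lower first-day value if the target is the newborn.
2. Add a case using each woman's highest interval concentration.
3. Divide by each woman's actual dose in mg/kg/day and correct the printed mg/day denominator. Read literally, that denominator would turn 1.25% into 0.018% for a 70 kg woman (1.25/70). The actual dose is needed because the cap brings it below 1.2 mg/kg above 80 kg.
4. State a rule for collection intervals that yield no milk, and report how many there were.
5. Report the concentration × collected-volume figure only as amount recovered in expressed milk, with each woman's 24-hour volume beside it.

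No infant weight is then needed.

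The cost is SAP wording and a recalculation from concentrations already measured and labelled by collection time. The downsides are that RID then rests on an explicit intake assumption, will usually be higher than the SAP's figure, and may need interpolation for women with very low output.

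### The RID formula divides an infant dose per kg by a maternal dose that is not per kg, so as written RID is too small by the mother's weight in kg and the 10% cut-off loses its meaning

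*SAP*

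**What the plan says.** SAP section VII describes the calculation in three steps. Concentrations of ketamine and its metabolites in milk are "converted to amount by multiplying with the volume of breast milk collected at various time intervals". These amounts, with metabolites as molar equivalents, are added up to a cumulative dose. RID is then obtained from the displayed formula, "RID (\%) = \text{Cumulative infant dose via breast milk} \left(\frac{\text{mg}}{\text{kg}} \right) \times 100 \div \text{maternal dose} \left(\frac{\text{mg}}{\text{day" (typeset source), whose numerator is in mg/kg and whose denominator is in mg/day. The result is judged against one cut-off: "An RID $\leq 10\%$ was considered low".

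The maternal dose comes from SAP section II: "sub-anesthetic ketamine infusion at 0.1 mg/kg/hour for 12 hours (not to exceed 8mg/hr dose". Section III gives the milk collection window, "starting at the time of infusion initiation (t_0) and ending 12 hours after the infusion was stopped (t_{24", which is 24 hours. Section VIII lists maternal weight among the recorded characteristics. Neither document divides the maternal dose in the RID by that weight, and neither gives an infant weight.

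**The concern.** A relative dose compares two doses on the same scale. Here the upper one is per kg of body weight and the lower one is a whole-body total. Their ratio has units of (mg/kg)/(mg/day) = day/kg, and its size depends on how heavy the mother is. It cannot be read against a 10% limit.

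The direction matters. Leaving out the division by maternal weight makes the denominator too large, so the error can only make exposure look smaller. RID is the only infant-exposure measure in the SAP, and 10% is its only cut-off for calling exposure low; the milk-to-plasma ratio in section VI is interpreted around 1 but carries no acceptability limit. The protocol's hypothesis (Study Aims) is that secretion into milk is low with minimal neonatal risk. Its Brief Description says Part 1 will inform whether breastfeeding pairs are admitted to the later trial. The documents do not name RID as the basis for that decision. That RID would weigh in it is an inference, though a natural one.

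**Working it through.** The plan states no RID value, so there is no figure to reproduce. The check is on the formula.

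**Inputs from the documents**
- Infusion of 0.1 mg/kg/h for 12 h, at most 8 mg/h (SAP II).
- Milk collected over 24 h (SAP III).
- Cut-off of 10% (SAP VII).
- Assay linear from 0.05 to 100 ng/mL (SAP IV), used only in the last step.

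**Assumptions, because the documents give no values:** maternal weight W of 50 to 100 kg and infant weight w of 3.5 to 10 kg.

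**Step 1: maternal dose.** D = min(0.1 x W, 8) x 12 mg. The cap applies above 80 kg.

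**Step 2: the two versions of RID.** Let A be the mg of drug in milk over the 24 h.
- As printed: 100 x (A/w) / D
- Both sides per kg: 100 x (A/w) / (D/W)

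The second divided by the first is exactly W, with or without the cap. The absence of a per-day unit in the numerator has no numerical effect, because milk is collected over one day and the whole dose falls within it. Only the missing maternal kg matters.

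**Step 3: what the cut-off means as printed.** A per-kg RID of 10% prints as 10/W %. A printed 10% is a per-kg RID of 10 x W %.

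| W (kg) | D (mg) | D/W (mg/kg) | Per-kg RID of 10% prints as | Printed 10% needs an infant dose of | Per-kg RID at that point |
|---|---|---|---|---|---|
| 50 | 60 | 1.20 | 0.20% | 6.0 mg/kg | 500% |
| 70 | 84 | 1.20 | 0.14% | 8.4 mg/kg | 700% |
| 80 | 96 | 1.20 | 0.125% | 9.6 mg/kg | 800% |
| 100 | 96 | 0.96 | 0.10% | 9.6 mg/kg | 1000% |

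At 70 kg: 10% of 1.2 mg/kg is 0.12 mg/kg, and 0.12 x 100 / 84 = 0.14%. In the other direction, 8.4 x 100 / 84 = 10%, and 8.4 / 1.2 = 7, which is 700%.

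**Step 4: drug needed in milk to reach 10%.** As printed, A = 0.10 x w x D, so the share of the maternal dose is 0.10 x w whatever the mother's weight: 35% for a 3.5 kg infant, 50% for 5 kg and 100% for 10 kg. With both sides per kg and a 70 kg mother, A = 0.12 x w: 0.42, 0.60 and 1.2 mg, which are 0.5%, 0.7% and 1.4% of the 84 mg given.

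**Step 5: would a corrected RID pass 10%?** Suppose all milk is at the assay's upper limit of 100 ng/mL and the volume is an assumed 1000 mL, so A = 0.1 mg for one analyte. The highest value in the assumed range is at W = 100 and w = 3.5: 100 x (0.1/3.5) / 0.96 = 3.0%. Three analytes added by mass, without molar correction, give 8.9%. The printed formula gives 0.03% and 0.09% for the same milk.

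**The case against.** The strongest reply is that this may be a slip in the printed units and not in the calculation. Each side lacks one part, per day above and per kg below, which fits an intended mg/kg/day on both sides. Stacked fractions may also have lost a unit when the PDF was read. With no RID value or worked example to check, an actual understatement is not shown. This stands as a limit: the factor W is conditional on the formula being used as printed. It does not remove the point, because section VII states that RID was calculated with this formula and nothing elsewhere in the documents corrects it.

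A second reply is that the conclusion may not change. Under the assumptions of step 5, a corrected RID stays below 10%. This also stands, with the caution that diluted samples above the linear range could exceed that bound. But 8.9% is close to the limit while 0.09% looks negligible, and a favourable true value would not make the printed test a valid one.

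A third reply is that the primary outcome, milk concentration, is untouched, as are the milk-to-plasma ratios and the PK parameters. That is correct; the fault is confined to RID.

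Finally, a corrected formula needs an infant weight that the plan never defines. This is so, but the SAP's own mg/kg numerator already needs one if it means infant kg. It is a gap to close in the same edit.

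**Conclusion.** The concern holds. As written, RID is not a percentage and is too small by exactly the mother's weight in kg: 50- to 100-fold for assumed weights of 50 to 100 kg. The 10% cut-off then trips only if 35% to 100% of the whole maternal dose reaches the milk within 24 hours, for assumed infants of 3.5 to 10 kg. Such a limit cannot separate low from high exposure, and the error runs only towards reassurance.

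The result rests on the formula being applied as printed and on the numerator's kg being the infant's. The documents do not show that any computed RID is wrong, or that a corrected one would exceed 10%. The formula must be corrected in either case, because it is the stated method for the SAP's only measure of infant exposure.

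**What to change.** Replace the formula in SAP section VII with:

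RID (%) = 100 x infant dose (mg per kg infant per day) / maternal dose (mg per kg mother per day)

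- Take the maternal dose as the mg actually infused over the 12 hours divided by the mother's weight. The nominal 1.2 mg/kg should not be used above 80 kg: at 100 kg the capped dose is 0.96 mg/kg, and 0.96/1.2 = 0.80, so the nominal figure would understate RID by 20%.
- State the infant weight used and its source, and show how RID changes with it. Across 3.5 to 10 kg it changes by a factor of 10/3.5 = 2.9.
- State which units were used in any RID already produced. Recompute those that followed the printed formula before comparing them with 10%.

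The cost is one corrected formula, one added definition and a recalculation. Maternal weight is already recorded and the dose follows from the infusion. The infant weight is the one input the plan does not yet supply. If the printed formula was used, the reported RID will rise by a factor equal to each mother's weight in kg.
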